## 7.4 Vital Signs

Blood pressure, heart rate, and respiratory rate will be measured in a sitting position after at least 5 minutes of sitting (except for safety reasons).

In Part 1 of the study (SAD), blood pressure, heart rate, and respiratory rate will be measured at screening, in the morning on Day -1, pre-dose, approximately 1, 2, 4, 6, 8, 12, 24, and 48 hours post-dose, and on Day 4. Body temperature will be measured at screening, Day -1, and Day 4. In Part 2 of the study (MAD), blood pressure, heart rate, and respiratory rate will be measured screening, in the morning on Day -1, pre-morning dose every day (Days 1 to 13), approximately 1, 2, 4, 6, 8, and 12 hours post-morning dose on Day 1 and Day 13, approximately 2 and 6 hours post-morning dose on Days 2 to 12, and once on Days 14, 15, and 16. Body temperature will be measured at screening, Day -1, and Day 16.

When vital signs measurements coincide with a blood draw, they should preferably be performed before the blood collection whenever possible. A time window of 15-20 minutes for vital signs will be allowed if there are multiple procedures at the same time point.

A listing of all vital signs results will be provided.

Descriptive statistics (mean, median, SD, Min, Max, and sample size “n”) for each vital sign measurement will be presented considering each study part separately, by cohort and group for each time point. Change from baseline descriptive statistics for all post-dose time points will also be presented. Baseline will be defined as the last results (scheduled or unscheduled) obtained prior to drug administration in each part/cohort.

Results from unscheduled or repeat tests will not be included in the summary statistics unless the repeat was required (and documented as such) due to technical reasons or an invalid initial result, or for baseline determination if applicable.

## 7.5 Pulse Oximetry

Pulse oximetry will be performed at the screening visit. Baseline continuous pulse oximetry will be performed during the nighttime of Day -1 (minimum of 8 hours prior to first dose administration).

For Part 1 of the study (SAD), following the dose and throughout study conduct, oxygen saturation will be measured via pulse oximetry at pre-dose and 1.5, 4.5, and 8 hours post-dose. Oxygen saturation will be monitored via continuous pulse oximetry overnight beginning at bedtime and until awaking the next morning from Day 1 to end of confinement with oxygen saturation measurements specifically recorded at approximately midnight and 4 am.

For Part 2 of the study (MAD), following the first dose and throughout study conduct, oxygen saturation will be measured via pulse oximetry at pre-morning dose, at 1.5, 4.5, and 8 hours following the morning dose, and at 2 hours following the evening dose. Oxygen saturation will be

monitored via continuous pulse oximetry beginning at bedtime and until awaking the next morning from Day 1 to end of confinement with oxygen saturation measurements specifically recorded at approximately midnight and 4 am.

Pulse oximetry measurements may be collected within 10 minutes before or after the specified time point.

A listing of all Pulse oximetry results will be provided.

## **7.6 12-lead Electrocardiogram**

For Part 1 of the study (SAD), a 12-lead ECG will be performed at screening, in the morning on Day -1, pre-dose, approximately 1, 2, 4, 6, 8, 12, 24, and 48 hours post-dose, and on Day 4.

For Part 2 of the study (MAD), a 12-lead ECG will be performed at screening, in the morning on Day -1, pre-morning dose every day (Days 1 to 13), approximately 1, 2, 4, 6, 8, and 12 hours post-morning dose on Day 1 and Day 13, and once on Days 14, 15, and 16.

ECG will be performed after a resting time of at least 5 minutes in supine position. When ECG coincides with a blood draw, it should preferably be performed before the blood collection whenever possible. A time window of 15-20 minutes for ECGs will be allowed if there are multiple procedures at the same time point.

A listing of all ECG results will be provided.

Descriptive statistics (mean, median, SD, Min, Max, and sample size “n”) for each measurement (continuous variables) will be presented considering each study part separately, by cohort and group for each time point. Change from baseline descriptive statistics all post-dose time points will also be presented. Baseline will be defined as the last results (scheduled or unscheduled) obtained prior to drug administration in each part and cohort. Results from unscheduled or repeat tests will not be included in the summary statistics unless the repeat was required (and documented as such) due to technical reasons or an invalid initial result, or for baseline determination if applicable.

## **8. Pharmacokinetic Analyses**

### **8.1 General PK Considerations**

- All samples from nalbuphine-dosed subjects will be analyzed and all concentrations listed.
- The listing of PK concentrations will be flagged for subjects who did not receive all doses and any other significant protocol deviations.
- Subjects missing one dose of scheduled IP or experiencing emesis during the study will be evaluated on a case-by-case basis for possible impact on the outcome of the study.
- Descriptive statistics will be performed for all time points available, with the exclusion of subjects who did not receive all doses or any other significant protocol deviations.
- Pharmacokinetic parameters will be derived where possible for all subjects. Data from subjects with incomplete profiles (missed blood draws, lost samples, samples unable to be quantified) may be used if PK parameters can be estimated using the remaining data points.
- Descriptive statistics will be performed on all parameters available, and any missing parameters will be flagged.

### **8.2 Handling of the BLQ and the No Reportable Concentration Values**

All concentration values below the lower limit of quantitation (BLQ) and samples with no reportable value occurring prior to the first dosing will be replaced by “0.00”. For tabulation, graphical representation and calculation purposes, all samples with no reportable value observed after administration of the first dosing will be set to missing.

### **8.3 Handling of the Difference between the Scheduled and the Actual Sampling Times**

The actual clock time for dosing and the actual clock time for each collection time for the PK samples will be recorded. For all sampling times, the actual sampling times will be calculated as the difference between the sample collection actual clock time and the actual clock time of dosing. The actual post-dose sampling times expressed in hours and rounded off to three decimal digits will be used to calculate the PK parameters, except for pre-dose samples occurring prior to dosing, which will always be reported as zero (0.000), regardless of the time difference. In the PK section of the report, scheduled sampling times will be presented in concentration tables and mean graphs while actual times will be presented for the individual graphs. A listing of the actual times will be provided for PK samples.

## 8.4 Pharmacokinetic Concentration and Parameters

### 8.4.1 Part 1 (SAD) - Cohort 1 to 5

A total of 11 blood samples will be drawn for quantification of nalbuphine and its metabolites (if required) from each subject for PK analyses. Blood samples will be collected prior to drug administration and at 1.50, 3.00, 5.00, 7.00, 9.00, 12.0, 24.0, 36.0, 48.0, and 72.0 hours post-dose.

Plasma concentrations from nalbuphine and its metabolites (if required) will be used to calculate the following parameters by standard non-compartmental methods:

AUC 0-t :	Area under the concentration-time curve from time zero to the last measurable concentration.
AUC 0-inf :	Area under the concentration-time curve from time zero to infinity, calculated as AUC 0-t + C t /K el , where: C t = the last measurable concentration.
C max :	Maximum observed concentration.
T max :	Time of observed C max .
T ½ el :	Terminal elimination half-life, calculated as ln(2)/K el .
Residual area	Calculated as 100*(1 - AUC 0-t / AUC 0-inf ).
Cl/F:	Apparent total body clearance, calculated as Dose/AUC 0-inf for nalbuphine.
V d /F:	Apparent volume of distribution during terminal phase, calculated as Dose/(K el x AUC 0-inf ) for nalbuphine.
K el	Elimination rate constant. This parameter will be the negative of the estimated slope of the linear regression of the ln-transformed concentration versus time profile in the terminal elimination phase. At least 3 concentration points will be used in estimating K el . C max should not be used in this estimation unless there are only two other quantifiable concentrations available following the C max . The time point where log-linear K el calculation begins (K el Lower ), and the actual sampling time of the last quantifiable concentration used to estimate the K el (K el Upper ) will be reported with the correlation coefficient from the linear regression to calculate K el .

### 8.4.2 Part 2 (MAD) – Cohort 6

On Day 1 a total of 10 blood samples will be drawn for quantification of nalbuphine and its metabolites in plasma from each subject for PK analyses as follows:

- At Day 1 – Pre-dose and at 1.50, 3.00, 4.00, 5.00, 6.00, 7.00, 9.00, 12.0, and 24.0 hours post-dose.

On Days 4, 7 and 10 a total of 9 blood samples will be drawn for quantification of nalbuphine and its metabolites in plasma from each subject for PK analyses as follows:

- At Day 4, 7 and 10 – pre-morning dose and at 1.50, 3.00, 4.00, 5.00, 6.00, 7.00, 9.00, and 12.0 hours post-dose (prior to the evening dose administration).

On Day 13 a total of 12 blood samples will be drawn for quantification of nalbuphine and its metabolites in plasma from each subject for PK analyses as follows:

- At Day 13 – pre- dose and at 1.50, 3.00, 5.00, 7.00, 9.00, 12.0, 24.0, 36.0, 48.0, 72.0 and 96.0 hours post- last dose.

Trough blood samples will be collected on Days 2, 3, 5, 6, 8, 9, 11, 12, and 13 prior to the morning and evening (if applicable) dose administrations.

Plasma concentrations on Day 1 from nalbuphine and its metabolites will be used to calculate the following parameters by standard non-compartmental methods:

- AUC0-12: Area under the concentration-time curve from time zero to 12 hours.
- AUC0-24: Area under the concentration-time curve from time zero to 24 hours.
- Cmax: Maximum observed concentration.
- Tmax: Time of observed Cmax.

Plasma concentrations on Days 4, 7 and 10 from nalbuphine and its metabolites will be used to calculate the following parameters by standard non-compartmental methods:

- AUC0-12: Area under the concentration-time curve from time zero to 12 hours.
- Cmax: Maximum observed concentration.
- Tmax: Time of observed Cmax.

Plasma concentrations on Day 13 will be used to calculate the following parameters by standard non-compartmental methods:

- AUC0-12: Area under the concentration-time curve from time zero to 12 hours.
- AUC0-24: Area under the concentration-time curve from time zero to 24 hours.
- AUC0-t: Area under the concentration-time curve from time zero to the last measurable concentration.
- AUC0-inf: Area under the concentration-time curve from time zero to infinity, calculated as AUC0-t + Ct/Kel, where: Ct = the last measurable concentration.
- Cmax: Maximum observed concentration.
- Ctrough: Concentration at the end of one dosing interval (tau = 12 hours)

$T_{max}$ :	Time of observed $C_{max}$ .
Fl (%):	Percentage of fluctuation ( $100 * (C_{max} - C_{tau}) / C_{avg}$ Where $C_{tau}$ is $C_{trough}$ and $C_{avg}$ is equal to $AUC_{tau}/tau$ or $AUC_{0-12}/12$ hours in the current study.
Residual area	calculated as $100 * (1 - AUC_{0-t} / AUC_{0-inf})$
$T_{1/2 el}$ :	Terminal elimination half-life
$K_{el}$	Elimination rate constant. This parameter will be the negative of the estimated slope of the linear regression of the ln-transformed concentration versus time profile in the terminal elimination phase. At least 3 concentration points will be used in estimating $K_{el}$ . $C_{max}$ should not be used in this estimation unless there are only two other quantifiable concentrations available following the $C_{max}$ . The time point where log-linear $K_{el}$ calculation begins ( $K_{el Lower}$ ), and the actual sampling time of the last quantifiable concentration used to estimate the $K_{el}$ ( $K_{el Upper}$ ) will be reported with the correlation coefficient from the linear regression to calculate $K_{el}$ .
Cl/F:	Apparent total body clearance, calculated as $Dose / AUC_{0-inf}$ for nalbuphine.
$V_d/F$ :	Apparent volume of distribution during terminal phase, calculated as $Dose / (K_{el} * AUC_{0-inf})$ for nalbuphine.

Additional PK analysis may be performed. Upon the Sponsor's request, PK repeats might be performed. If re-assays are requested for PK reasons, final results will include re-assay values, while results with original values will be presented in an appendix of the report as supportive data.

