Nalbuphine exposure increased with increasing dose in a near proportional manner upon repeated dosing. In this multiple-dose study (TR01), subjects were titrated every 3 to 4 days from 27 mg once per day on day 1, to 27 mg twice daily then 54 mg twice daily, 108 mg twice daily, and finally 162 mg twice daily over a 13-day period. Steady state seemed to be reached within 2 to 3 days of dosing with a modest accumulation in exposure (accumulation factor [R] = 1.6) and no evidence of unexpected accumulation (See [Table 2](#)).

The presence of food (high-fat-high-calorie meal) did not affect the extent of absorption (AUC) or T_{max} for the current formulation of NAL ER tablets. However, the C_{max} values were about 1.5-fold higher in the fed than the fasted state.

Table 2 Summary of Mean Pharmacokinetics Parameters (N = 7 to 9) Following Multiple Escalating Oral Doses of NAL ER Tablets in Healthy Subjects (Clinical Study TR01)

Parameter	Descriptive Statistics	Healthy Subjects ^a				
		27 mg qd	27 mg bid	54 mg bid	108 mg bid	162 mg bid
		(Day 1)	(Day 4)	(Day 6)	(Day 9)	(Day 13)
AUC _{0-∞} (h·ng/mL)	n	7	—	—	—	8
	Mean	49.53	—	—	—	588.4
	SD	30.04	—	—	—	214.08
	CV%	60.7	—	—	—	36.4
AUC _{tau} (h·ng/mL)	n	9	9	9	9	8
	Mean	31.53	50.88	106.11	240.37	351.15
	SD	16.93	27.54	50.49	93.68	118.21
	CV%	53.7	54.1	47.6	39	33.7
ARAUC _{tau}	—	1.61	—	—	—	—
C _{max} (ng/mL)	n	9	9	9	9	8
	Mean	5.2	6.45	13.46	28	44.21
	SD	2.78	3.58	6.43	11.49	14.54
	CV%	53.5	55.5	47.8	41	32.9
T _{max} (h)	n	9	9	9	9	8
	Min	2	2	2	3	2
	Median	3	2	3	5	4
	Max	5	6	6	9	6
T _{1/2} (h)	N	7	—	—	—	8
	Mean	6.81	—	—	—	8.58
	SD	2.79	—	—	—	2.05
	CV%	41	—	—	—	23.9

ARAUC_{tau} = mean AUC_{tau} day 4/mean AUC_{tau} day 1; AUC = area under the curve; — AUC_{0-∞} = area under the curve from time 0 extrapolated through infinity; AUC_{tau} = AUC_{0-12h}; bid = twice daily; C_{max} = maximum plasma concentration; CV = coefficient of variation; qd = once per day; T_{1/2} = half-life; T_{max} = time of maximum concentration; — = not applicable.

^a = Subjects were dosed with multiples of 27 mg tablets.

Source: Investigator's Brochure Nalbuphine Extended-Release Tablets.

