5.2.1 Rationale for a Single- and Multiple-Escalating Dose Design

This study will include both a single-ascending-dose (SAD) portion and a multiple-ascending dose (MAD) portion. The PK, safety, and tolerability of single ascending doses (SAD) of NAL ER (4 dose levels) will be evaluated in subjects with mild and moderate hepatic impairment. Severe hepatic subjects will be evaluated at a single dose of 27 mg.

The purpose of the SAD will be to assess the safety and PK parameters of the given dose levels in hepatic impaired subjects relative to a selected healthy subject control population as part of the overall NAL ER development program. The SAD will also allow a better understanding of the safety, tolerability and expected steady state PK characteristics in mild and moderate hepatic impairment prior to undertaking safety and itch suppression efficacy studies in this patient population.

In the MAD portion of this study, PK assessment will be carried out at steady state at each respective dose level at steady state during the titration over 13 days up to the highest planned therapeutic dose of 162 mg. It is well documented, in clinical practice and the opiate literature, that gradually increasing the dose of drug with a structured titration can reduce the frequency and severity of the expected AEs associated with initiation of therapy. The NAL ER clinical program utilizes this type of structured titration strategy, starting with once per day dosing at the 27 mg dose of NAL ER, and increasing the dose in a stepwise manner over the next 13 days to the target investigational dose of 162 mg twice daily. Pharmacokinetic steady state is reached after 2 to 3 days of 162 mg twice daily.

Once the Part 1 SAD portion of the study is completed, if in the judgement of the Safety Committee the PK data demonstrates dose linearity across the dose range in both the mild and moderate hepatic impairment subjects (Group 1 and Group 2 subjects), such that PK modeling can be predictive of steady state dosing levels, a decision may be made to end the study without conducting Part 2 of the study.

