Based on the overall safety and tolerability observed in the subjects with mild and moderate impairment, at the completion of all doses tested, it will be determined by the Safety Committee whether or not it is safe to proceed with dosing for the first 2 subjects with severe Impairment. After review of the safety and tolerability for the first 2 severe subjects dosed at 27 mg, it will be determined whether or not to complete that dose level for the remaining severe subjects.

At the completion of all subjects dosed in the cohort, there will be an evaluation of safety and tolerability to determine whether to proceed to the next dose level for this group.

The Safety Committee will be composed of at least the Investigators and one medically qualified Sponsor representative. Some adjustments to the currently outlined doses and/or dosing regimen may be implemented by the Safety Committee, but the dose to be administered in a given dose cohort will not exceed the one currently outlined in the protocol.

Drug administration in Part 2 of the study (MAD) may be initiated following satisfactory review of the safety and tolerability data from Groups 1 and 2 (mild and moderate impairment) from Part 1 of the study (SAD) by the Safety Committee. Depending on safety and tolerability as well as on available PK data, the dose escalation scheme may be modified such that intermediate dose levels are administered. The dosage regimen (once daily versus twice daily) will be confirmed following review of PK data from Part 1 of the study (SAD).

If in the judgement of the Safety Committee the Part 1 PK data demonstrates dose linearity across the dose range in both the mild and moderate hepatic impairment subjects (Group 1 and Group 2 subjects), such that PK modeling can be predictive of steady state dosing levels, a decision may be made to end the study without conducting Part 2 of the study

In Part 2 of the study (MAD), subjects will receive a single 27 mg dose in the morning of Day 1. Starting on Day 2, doses will be subsequently escalated for each subject to twice daily, 12 hours apart, 27 mg, 54 mg, 108 mg, and 162 mg over 13 days. On the last treatment day, (Day 13), subjects will receive a single 162 mg dose in the morning. Subjects will remain at each dose level for 2-3 days (minimum 5 consecutive doses) with dose escalation predicated on tolerability of the prior dose (See Section [9.14.4](#) for dose escalation stopping rules).

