12.1 Pharmacokinetics

The following pharmacokinetic parameters will be calculated by standard non-compartmental methods for nalbuphine and metabolites (if required).

Part 1 (SAD):

- 1) AUC_{0-t} : area under the concentration-time curve from time zero to the last non-zero concentration
- 2) AUC_{0-inf} : area under the concentration-time curve from time zero to infinity (extrapolated)
- 3) C_{max} : maximum observed concentration
- 4) T_{max} : time of observed C_{max}
- 5) $T_{1/2\text{ el}}$: elimination half-life
- 6) Residual area: calculated as $100 \times (1 - AUC_{0-t} / AUC_{0-inf})$
- 7) K_{el} : elimination rate constant
- 8) Cl/F : apparent total body clearance of the drug from plasma
- 9) V_d/F : apparent volume of distribution, calculated as $Dose / (K_{el} \times AUC_{0-inf})$

Part 2 (MAD), Day 1:

- 1) AUC_{0-12} : area under the concentration-time curve from time zero to the 12-hour period
- 2) AUC_{0-24} : area under the concentration-time curve from time zero to the 24-hour period
- 3) C_{max} : maximum observed concentration
- 4) T_{max} : time of observed C_{max}

Part 2 (MAD), Days 4, 7, and 10:

- 1) AUC_{0-12} : area under the concentration-time curve from time zero to the end of the dosing period
- 2) C_{max} : maximum observed concentration
- 3) T_{max} : time of observed C_{max}

Part 2 (MAD), Day 13:

- 1) AUC_{0-12} : area under the concentration-time curve from time zero to the 12-hour period
- 2) AUC_{0-24} : area under the concentration-time curve from time zero to the 24-hour period
- 3) AUC_{0-t} : area under the concentration-time curve from time zero to the last non-zero concentration
- 4) AUC_{0-inf} : area under the concentration-time curve from time zero to infinity (extrapolated)
- 5) C_{max} : maximum observed concentration
- 6) C_{trough} : last observed concentration
- 7) T_{max} : time of observed C_{max}

- 8) Fl(%): percentage of fluctuation
- 9) Residual area: calculated as $100 \times (1 - AUC_{0-t} / AUC_{0-inf})$
- 10) $T_{1/2\text{el}}$: elimination half-life
- 11) K_{el} : elimination rate constant
- 12) Cl/F: apparent total body clearance of the drug from plasma
- 13) V_d/F : apparent volume of distribution, calculated as $\text{Dose} / (K_{el} \times AUC_{0-inf})$

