
- Inter Subject CV =  $100 * \text{SQRT}(e^{[MSE]} - 1)$ ;
- Ratio =  $100 * e^{\text{DIFFERENCE}}$ , where DIFFERENCE is the point estimate of hepatic impairment groups difference (e.g. Mild – Control, Mild – Control, and Severe - Control) on the ln-transformed scale; and
- 90% Confidence Limits =  $100 * e^{(\text{DIFFERENCE} \pm t_{(dfResidual)} * SE_{\text{DIFFERENCE}})}$ .

Sample code for the procedure in SAS® for nonparametric comparison (Mild vs Control):

```
proc npar1way hl alpha=.10 data= basepk;
  where GROUP in ('1','4');
  class GROUP;
  var Tmax;
  exact hl;
  ods select WilcoxonScores HodgesLehmann;
run;
```

Within each group, dose proportionality will be assessed by a visual assessment of the individual and mean nalbuphine PK parameters.

In the event that hepatic impairment has a clinically relevant effect on nalbuphine PK, the relationship between hepatic impairment and appropriate PK parameters for nalbuphine (e.g., CL/F, AUC0-12, AUC0-24, AUC0-t, AUC0-inf, AUC0-t, Ctrough, and Cmax) will be determined by a linear or non-linear regression.

Study results including the graphical description and the relationships between hepatic impairment and relevant pharmacokinetic parameters will be used to elaborate specific dosing recommendations if deemed clinically relevant.

Additional and exploratory statistical analysis may be performed.

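### Day 13 CL/F and Vd/F use the single-dose formulas after repeated dosing, and come out about 40% too low on the TR01 means

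*SAP*

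**What the plan says.** SAP 8.4.2, in its Day 13 list, gives CL/F as "Apparent total body clearance, calculated as $Dose / AUC_{0-inf}$ for nalbuphine" and Vd/F as "Apparent volume of distribution during terminal phase, calculated as $Dose / (K_{el} * AUC_{0-inf})$ for nalbuphine". The same two formulas appear in SAP 8.4.1 for the single-dose Part 1. Protocol 12.1, Day 13 list, has "apparent volume of distribution, calculated as" Dose/(Kel × AUC0-inf). It names CL/F for Day 13 but gives no formula for it. Neither document describes a correction for drug carried over from earlier doses.

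Day 13 ends a titration. On that day "subjects will receive a single 162 mg dose in the morning" (Protocol 9.4), after 162 mg twice daily on Days 11 and 12. Protocol 5.2.1 states: "Pharmacokinetic steady state is reached after 2 to 3 days of 162 mg twice daily".

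Elsewhere SAP 8.4.2 treats Day 13 as a steady-state interval. Ctrough is defined as "Concentration at the end of one dosing interval (tau = 12 hours"), and the average concentration in the fluctuation index is AUC0-12 divided by 12 hours.

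CL/F is used in SAP 8.5. If impairment has a clinically relevant effect, its relationship with PK parameters, CL/F among the examples, "will be determined by a linear or non-linear regression". Those relationships inform the dosing recommendations.

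**The concern.** Dose/AUC0-inf equals CL/F only when all the drug in the measured area comes from that dose. After repeated dosing it does not, so the ratio divides one dose by the exposure from several. At steady state one dose corresponds to the area over one dosing interval.

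Two readings of the results are at risk. Subjects may take part in both study parts, and their CL/F would appear to fall between Part 1 and Day 13 with no change in clearance. That could be taken for time-dependent kinetics. Also, because the carried-over share rises with half-life, any difference in half-life between the mild and moderate groups would enter the comparison of their Day 13 CL/F and Vd/F.

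**Working it through.** **Inputs.** Protocol 5.1.1.2, Table 2 (TR01, healthy subjects; areas in h·ng/mL, AUCtau = AUC0-12): AUCtau 31.53 on Day 1, 50.88 on Day 4 and 351.15 on Day 13; AUC0-∞ 49.53 on Day 1 and 588.4 on Day 13; Day 13 Cmax 44.21 ng/mL and half-life 8.58 h. Day 13 values have n = 8. Table 1: AUC0-∞ 328 after a single fasted 162 mg dose.

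**1. The documents' own figure.** The protocol reports a "modest accumulation in exposure (accumulation factor [R] = 1.6"). Table 2 gives 50.88/31.53 = 1.614, which reproduces the tabulated 1.61. Carry-over between doses is therefore material.

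**2. Position of the Day 13 dose.** In the titration table (Protocol 9.4, SAP Table 3-2) the 162 mg doses fall on Day 10 PM, Day 11 AM and PM, Day 12 AM and PM, and Day 13 AM: six doses.

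**3. Size of the error.** Under linear kinetics at steady state, CL/F = Dose/AUCtau, so the planned value divided by the true value is AUCtau/AUC0-inf.
- Planned: 162,000/588.4 = 275 L/h.
- Interval-based: 162,000/351.15 = 461 L/h.
- Ratio: 351.15/588.4 = 0.597, an understatement of 40.3%. Converting the means to geometric means with the tabulated CVs (33.7% and 36.4%, log-normal assumed) gives 39.8%.
- Vd/F with Kel = ln2/8.58: about 3,410 L against about 5,710 L, the same proportion.

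**4. Two checks.**
- Single-dose CL/F from Table 1 is 162,000/328 = 494 L/h, near 461 and far from 275.
- A clearance of 275 L/h with 162 mg every 12 h implies an average concentration of 588.4/12 = 49.0 ng/mL. That is above the mean Cmax of 44.21 ng/mL, which is impossible for an average.

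**5. Dependence on half-life.** With one compartment and instantaneous input, the understatement at steady state is exp(−ln2 × 12/t½). The last column assumes first-order absorption at 0.3 per hour. Half-lives beyond those reported in healthy subjects (up to 9.6 h) are assumptions.

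| t½ (h) | Instantaneous input | Absorption 0.3/h |
|---|---|---|
| 6.8 | 29% | 38% |
| 8.58 | 38% | 45% |
| 12 | 50% | 55% |
| 17.16 (doubled) | 62% | 65% |
| 24 | 71% | 73% |

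Superposing the actual 13-day schedule changes these by at most about 1.5 percentage points.

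**6. Does the replacement work on this schedule?** In the same model, Dose/AUC0-12 on Day 13 overstates CL/F by 0.1% at 8.58 h, about 2% at 17.16 h and 5 to 6% at 24 h.

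**7. Where it would not work.** After a first dose, Dose/AUC0-inf is right and the interval form is wrong. On Day 1 of Table 2, 27,000/49.53 = 545 L/h against 27,000/31.53 = 856 L/h, 57% too high (means of 7 and 9 subjects). After the first 54 mg dose following 27 mg twice daily, neither form works. With t½ 8.58 h and instantaneous input, the fraction remaining after 12 h is 0.379.
- Area over 12 h, in units of 1/(CL/F): 54 × 0.621 + 27 × 0.379 = 43.8. Dose/AUC0-12 is 54/43.8 = 1.23 times the truth.
- Area to infinity: 54 + 27 × 0.379/0.621 = 70.5. Dose/AUC0-inf is 54/70.5 = 0.77 times the truth.

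**The case against.** The best defence is that little depends on this number. CL/F is in no Part 2 ANOVA; SAP 8.5 analyses AUC0-12, AUC0-24, Cmax and Ctrough directly, and the formula does not touch those. The regression is conditional, CL/F is one of several examples, and Day 13 is not specified. Part 1 CL/F is correctly defined, and the ratios to healthy controls come from Part 1 AUC and Cmax. Protocol 9.14.5 allows the study to end without Part 2. All of this stands. It limits the reach of the error but does not make the formula right.

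A second defence concerns the evidence. TR01 moved up every 3 to 4 days, while this study spends 2 to 3 days per level, so the regimens are similar but not identical. The single-dose check crosses studies and uses arithmetic means with wide spread (SD 165 on 328). These points affect the precision of the 40%, not its direction.

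A reader might infer that the formula inflates the impairment effect, for example that a true CL/F ratio of 0.50 against healthy subjects would be reported as 0.50 × 1.61/2.60 = 0.31, where 1.61 and 2.60 are the one-compartment values of AUC0-inf/AUCtau at 8.58 h and 17.16 h. The documents do not support that as a finding. Part 2 has no healthy control, so no such ratio is planned. The doubled half-life is hypothetical: Protocol 5.2.2 says only that times may be longer in patients, citing general guidance and giving no size. If impairment acted mainly through bioavailability, CL/F could fall with little change in half-life. The bias would then be about the same in both groups and largely cancel in their ratio.

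**Conclusion.** The Day 13 formulas are wrong as written: both CL/F and Vd/F are understated whenever earlier doses still contribute to the area. The size is about 40% on the TR01 means. That figure comes from eight healthy subjects and assumes linear kinetics and steady state on Day 13; it is not an estimate for Cohort 6. Day 13 CL/F will not be comparable with Part 1 CL/F. The mild versus moderate comparison of these two parameters is distorted if, and only if, half-life differs between the groups.

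The error should be corrected, but it does not threaten the study's main comparison. It affects two Day 13 parameters and any regression that uses them, provided Part 2 is run.

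**What to change.** In SAP 8.4.2, for Day 13, define CLss/F = Dose/AUCtau and Vz/F = Dose/(Kel × AUCtau). AUCtau is AUC0-12 under the planned twice-daily regimen, and the area over the actual interval if the regimen changes, since both documents leave once versus twice daily to be confirmed after Part 1. Report both parameters subject to the steady-state assessment in SAP 8.6. Make the same change to Vd/F in Protocol 12.1 and add the CL/F formula there. Keep Dose/AUC0-inf for Part 1.

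State a rule for the last-dose profiles of the DLT follow-up period (Protocol 9.11.1), because SAP 8.4.2 lists parameters only for Days 1, 4, 7, 10 and 13. Use the AUCtau form only where steady state at the last dose level is supported. Use Dose/AUC0-inf only after a first single dose. Otherwise do not report CL/F or Vd/F.

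The cost is wording in the SAP and the Day 13 CL/F and Vd/F entries in the protocol. AUC0-12 is already derived and no sample is added.
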